The participating sites are currently using valganciclovir prophylaxis for 100 days after liver transplantation for CMV prevention as standard of care with drug costs charged to the patient or third-party payers as part of routine clinical care. In this study, one group of subjects will continue to receive standard of care (valganciclovir prophylaxis) and the other group will receive preemptive therapy with valganciclovir only upon evidence of CMV infection. For the group randomized to preemptive therapy, the drug use is estimated to be 43% less. No additional costs for valganciclovir use for study purposes will be incurred by the participating institution, subject or another party for participants randomized to either preemptive therapy or to prophylaxis.

Use of model for end-stage liver disease (MELD) scoring system as the basis for prioritizing organ allocation by the United Network for Organ Sharing in the current era has led to a substantially higher number of patients undergoing transplantation who have renal dysfunction or are requiring dialysis than time in the previous years (53,54). In order that our study is considered representative of liver transplantation practices at present and in order for our findings to be generalized to the transplant population undergoing in current clinical settings, it is important to include liver transplant subjects that require dialysis. Data in patients on dialysis have documented no pertinent issues that could influence the pharmacokinetics and bioavailability of valganciclovir in the study subjects (55). Furthermore, all study sites are currently using valganciclovir in dialyzed patients as standard of care. Receipt of dialysis has no effect on CMV disease rate in transplant recipients. However, given higher post-transplant mortality in patients receiving dialysis (56), subjects will be stratified by receipt of dialysis and sample size calculations will take into consideration the mortality within the first year.

We propose to conduct a randomized trial comparing prophylaxis versus preemptive therapy for the prevention of CMV disease in R-/D+ liver transplant recipients. The key goals of the study are to assess the efficacy of the 2 clinically used approaches for CMV prevention and not the efficacy of the drug per se. In this regard, this is a strategy trial based on the clinical practice of medicine using a drug that is currently the standard of care in these patients.

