5.4.2 Randomization

Subjects will be randomized in 1:1 allocation to one of 2 study groups. All subjects that have met all criteria for study enrollment and have given written informed consent will be randomized via a web-based randomization system at the study web-portal.

The study team member randomizing the subject will get an immediate message providing group assignment. Randomization at each site will be stratified by: 1) the receipt of lymphocyte depleting induction and 2) dialysis at time of randomization. Randomization will occur as soon as it is feasible, but no later than 10 days after transplantation. Inadvertently randomized

subjects who do not meet the inclusion/exclusion criteria or those who are withdrawn prior to receiving the study drug will be replaced.

Subjects receiving lymphocyte depleting induction at the time of transplantation (even for those randomized to the preemptive therapy group) may receive up to 10 days of antiviral therapy with valganciclovir or IV ganciclovir after transplantation. Additionally, if the treating physician prescribes valganciclovir or IV ganciclovir for any length of time prior to randomization, it will not preclude subject enrollment. For subjects assigned to the prophylaxis group, the first dose of study drug should be given on the day of randomization regardless of lymphocyte induction. For subjects in the preemptive group that have received lymphocyte depleting induction, antiviral therapy with valganciclovir or IV ganciclovir will be given for ten days then stopped. Subjects that have not received lymphocyte depleting induction, but have received doses of valganciclovir or IV ganciclovir after transplantation prior to randomization, will have the pre-randomization treatment stopped and begin study treatment on randomization day based on their assigned group.

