12.6.1.5 Graft loss (loss due to retransplantation)

The incidence of retransplantation will be determined at the 3 and 12 month time points. The date of retransplantation will be considered the date of occurrence of the event. A Cochran-Mantel-Haenszel test stratified for receipt of antilymphocyte therapy and controlling for renal dialysis will be used to test the significance between the two treatment regimens.

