12.6.1.6 All-cause mortality

A Kaplan-Meier survival probability will be calculated for each regimen. The starting point will be the date of randomization and the end point will be date of death. Subjects will be censored at date of last follow up if lost to follow up, or at one year post-transplant. The equality of the two survivor functions will be compared using a rank sum test for both the non-stratified data as well as the stratified log rank test for each stratum separately (receipt of lymphocyte depleting induction therapy and renal dialysis). Graphs of the Kaplan-Meier curves will be presented.

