12.7 Exploratory end-points

12.7.1 Clinical outcomes

12.7.1.1 Time to onset of CMV disease

Disease free survival will be evaluated by calculating the Kaplan-Meier survival probability for each regimen. The starting point will be the day of transplant; the end point will be the date of onset of CMV disease. Subjects will be censored at date of death if unrelated to CMV, date of last follow up if lost to follow up or at end of study. Kaplan-Meier estimates of median time to onset of CMV disease and the associated 95% confidence interval will be presented. In addition, the Kaplan-Meier estimates and associated confidence intervals will be presented for specific time points (100-day, 6-month 12-months) and quartiles (25th and 75th). The study groups will be compared using the non-stratified log rank test, as well as the stratified log rank test for each stratum separately. Graphs of the Kaplan-Meier curves for each therapy group will be presented. The equality of the two survivor functions will also be compared using a Cox model adjusted for cluster [site] and controlled for receipt of anti-lymphocyte induction therapy and renal dialysis. The primary analysis will include assessment of baseline comparability between the two treatment groups. If needed, additional models will be developed to adjust for inequalities not adequately controlled by the randomization process. Results will be reported as the hazard ratio comparing the 2 groups. Survival analyses will also be controlled for unequal follow up periods between subjects. As such, the number of subjects available at annual time points will be reported, along with the Kaplan-Meier probability and associated 95% confidence intervals. It is assumed that subjects censored early will have the same probability of disease at each time point as those with longer follow up. To examine this assumption, relevant baseline characteristics will be compared between subjects enrolled in the first half of the study with those enrolled later. If the 2 cohorts are similar, we can expect that the survival probabilities are valid even with difference in follow up. Disease free survival will also be examined between the two cohorts.

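### All-cause mortality has no analysis using induction and dialysis together and no between-arm effect estimate, and its planned tests are ambiguously worded

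*Combined protocol and SAP*

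**What the plan says.** Section 12.6.1.6 (mortality to one year, a secondary outcome) plans Kaplan-Meier curves by regimen. It then names a rank sum test for the comparison of the two arms without strata. The same sentence goes on to a second comparison, which is the one in dispute here: "as well as the stratified log rank test for each stratum separately (receipt of lymphocyte depleting induction therapy and renal dialysis"). Section 12.7.1.6 (mortality to study closure, exploratory) repeats the sentence and adds confidence intervals for the annual Kaplan-Meier probabilities in each arm. Neither section plans a Cox model, a hazard ratio or any other between-arm estimate with a confidence interval.

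Section 5.4.2 sets the strata: "Randomization at each site will be stratified by: 1) the receipt of lymphocyte depleting induction and 2) dialysis at time of randomization". Section 2.2.2 gives the reason for the dialysis factor. It first says "Receipt of dialysis has no effect on CMV disease rate in transplant recipients", and then gives mortality as the ground for stratifying: "given higher post-transplant mortality in patients receiving dialysis (56), subjects will be stratified by receipt of dialysis".

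Elsewhere the plan does use both factors. For retransplantation, Section 12.6.1.5 says: "A Cochran-Mantel-Haenszel test stratified for receipt of antilymphocyte therapy and controlling for renal dialysis will be used". For time to CMV disease, Section 12.7.1.1 uses the same per-stratum log-rank phrase but also compares the arms "using a Cox model adjusted for cluster [site] and controlled for receipt of anti-lymphocyte induction therapy and renal dialysis".

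**The concern.** Dialysis was made a randomization factor because it predicts death, so mortality is the outcome where using that factor in the analysis matters most. As written, two statisticians could program different analyses from the same sentence. One might run a log-rank test inside each subgroup. Another might run one log-rank test stratified by induction and one stratified by dialysis. The rank sum label adds a further choice, because other sections name a log-rank test for the unstratified comparison of survival curves.

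Three things are at stake. The trial would have no designated adjusted mortality comparison and no estimate of the size of a mortality difference. Some power may be lost by ignoring a strong prognostic factor on which allocation was balanced. And if subgroup p-values are produced without being labelled descriptive, one of them could be read as a finding.

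**Working it through.** **The plan's own mortality figure.** The only mortality calculation is the halting-rule table in Section 9.8.3 (60 subjects, two-sided 0.05, power 0.90). Row 1: HR = ln(0.976)/ln(0.600) = 0.048. Freedman events = (1.960 + 1.282)² × ((1 + 0.048)/(1 − 0.048))² = 12.7, rounded up to 13, as stated. Row 2, at the stated HR of 0.089, gives 15.01, rounded up to 16, as stated. The table mentions no stratification, and the point here does not depend on it.

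**The two readings of the sentence.**

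| Reading | What is run | Pooled over strata? | Both factors in one comparison? |
|---|---|---|---|
| Stratum = subgroup | one test inside each subgroup | no | no |
| Stratum = factor | one pooled test by induction, one by dialysis | yes, one factor at a time | no |

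**Other outcomes.** Both factors are used for infections (12.6.1.3), rejection (12.6.1.4), retransplantation (12.6.1.5), neutropenia (12.6.2.1), adverse events (12.6.3) and time to CMV disease (12.7.1.1). They are also used for the two composites that include death (12.7.1.2 and 12.7.1.5). All-cause mortality lacks that step in both of its sections.

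**Size, by simulation.** The joint test is χ² = (Σ(Oₖ − Eₖ))² / ΣVₖ, summed over the four induction-by-dialysis cells. The unstratified test ignores the cells; I took it to be a log-rank test, because the rank sum test is not defined further. From the documents: 176 subjects, 1:1 allocation, two-sided 0.05, one-year follow-up. Not in the documents, so assumed: the shares on dialysis and induction, the mortality rates, the treatment effect, exponential survival, and no effect of induction on death.

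*Higher mortality* (10% at one year off dialysis in the better arm, treatment HR 2.5, 3,000 trials per row):

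| On dialysis / induction | Mortality on dialysis, better arm | Power, unstratified | Power, joint | Gain (points) |
|---|---|---|---|---|
| 15% / 25% | 30% | 73.9% | 76.6% | 2.7 |
| 15% / 25% | 45% | 72.2% | 80.5% | 8.3 |
| 25% / 40% | 30% | 77.7% | 81.6% | 3.9 |
| 25% / 40% | 45% | 79.6% | 88.0% | 8.4 |

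*Fewer deaths* (10% off dialysis in the worse arm, 10-30% on dialysis, 30% induction, dialysis HR 2 or 4, treatment HR 0.4, 4,000 trials each): power is 34-50% unstratified and 35-53% joint, a gain of 0 to 3 points. With 6% mortality off dialysis and 15% on dialysis, the gain is 0 to 1 point.

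**No treatment effect.** Rejection rates are 3-5% for the unstratified test and about 5-6% for the joint test, so both are acceptable.

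- *Subgroup reading.* At least one of four subgroup tests is significant in 13-19% of trials in the first two sets. As a check, four independent tests give 1 − 0.95⁴ = 18.5%. If only two subgroups hold enough deaths to matter, 1 − 0.95² = 9.8%. Hence roughly 10-19%. Power in the largest single cell is 36-48% in the higher-mortality set.
- *Factor reading.* The chance that any of the unstratified, dialysis-stratified or induction-stratified tests is significant is 4.6-5.4%, because the three are nearly the same test. In a separate run of the four higher-mortality rows (4,000 trials each), dialysis-only stratification has power 76.6, 82.0, 81.4 and 88.2%, against 76.6, 81.6, 81.3 and 87.8% for joint stratification. No power is lost.

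**The case against.** The strongest reply is that the parenthesis in the disputed sentence lists the two stratification factors, not subgroup levels, and that nothing is left to stratify inside a single subgroup. Read that way, the plan already has a pooled log-rank test stratified by dialysis, with essentially the power of the joint test and no inflation. This stands. A reader might infer that the plan has no pooled stratified mortality test at all, or that its false-positive rate is 15-19%. The documents do not support either as fact. Both need the subgroup reading, and the error rate also needs any significant subgroup to be claimed as a result, which the plan nowhere says.

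It also stands that the unstratified test is valid, that mortality is a secondary outcome (exploratory beyond one year), and that the largest power gains rest on high assumed mortality. In the higher-mortality set, the worse arm would have 29-37% one-year mortality. The documents give no one-year rate. Their allowance from 176 to 205 subjects for dropouts, withdrawals and deaths before six months (29/205, about 14%) covers a different window, but points lower.

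The jointly stratified composites do not answer the point, because they are different endpoints. Nor does the factor reading supply a comparison with both factors or an effect estimate.

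**Conclusion.** The point holds as a gap in specification. It is not an invalid test. On both readings no all-cause mortality analysis contains both randomization factors, and no hazard ratio with a between-arm interval is planned, although mortality is the stated reason for stratifying by dialysis. The wording also leaves open which tests will be run.

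The numerical cost is small to moderate and depends on rates that the documents do not give: about 0 to 8 power points, above 4 only in the scenarios with 45% mortality on dialysis. The false-positive chance of roughly 10-19% is conditional on the subgroup reading and on claiming any significant subgroup. If one pooled test per factor is meant, there is no such inflation and little power loss. The finding of substance is the missing combined comparison and effect estimate.

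**What to change.** In Sections 12.6.1.6 and 12.7.1.6, replace the rank sum and per-stratum wording with one named mortality comparison: a two-sided log-rank test stratified jointly by lymphocyte-depleting induction and dialysis at randomization, pooled over the strata. Add a Cox model stratified by the same two factors that reports the hazard ratio and its 95% CI. Within-stratum Kaplan-Meier results may stay, labelled supportive or descriptive.

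The same log-rank phrase in Section 12.7.1.1 can be aligned for consistency. That is less pressing, because a Cox model controlled for both factors is already planned there.

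The cost is a change of wording. It needs no new data, visits or subjects. A very small stratum simply contributes little information to the pooled test.

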12.6.2 Hematologic toxicity

12.6.2.1 Incidence of neutropenia

The incidence of neutropenia will be summarized for each of the following definitions of neutropenia: ANC values < 1000/ μ L and < 500/ μ L. Incidence will be determined based on safety labs performed per protocol. The analysis will be a CMH test of the significance of the odds ratio, while controlling for anti-lymphocyte antibody induction and renal dialysis with the levels of stratification determined at the time of randomization, using the modified ITT population. Results will be reported, as the MH odds ratio with 95% confidence intervals in the modified ITT population. The analysis will include assessment of baseline comparability of the comparison groups and will incorporate relevant items not adequately controlled by randomization in additional models.

12.6.3 Adverse events

Severe, unexpected drug related adverse events will be compiled and compared between the two groups. Adverse events will be evaluated by comparing the total number of reportable adverse events per person day of follow up between the two regimens. The analysis

will be repeated stratified by receipt of anti-lymphocyte induction and renal dialysis using Mantel-Haenzel weights. The analysis will include assessment of baseline comparability of the comparison groups and if necessary, will adjust for items not adequately controlled by randomization in additional models.

12.7 Exploratory end-points

12.7.1 Clinical outcomes

12.7.1.1 Time to onset of CMV disease

Disease free survival will be evaluated by calculating the Kaplan-Meier survival probability for each regimen. The starting point will be the day of transplant; the end point will be the date of onset of CMV disease. Subjects will be censored at date of death if unrelated to CMV, date of last follow up if lost to follow up or at end of study. Kaplan-Meier estimates of median time to onset of CMV disease and the associated 95% confidence interval will be presented. In addition, the Kaplan-Meier estimates and associated confidence intervals will be presented for specific time points (100-day, 6-month 12-months) and quartiles (25th and 75th). The study groups will be compared using the non-stratified log rank test, as well as the stratified log rank test for each stratum separately. Graphs of the Kaplan-Meier curves for each therapy group will be presented. The equality of the two survivor functions will also be compared using a Cox model adjusted for cluster [site] and controlled for receipt of anti-lymphocyte induction therapy and renal dialysis. The primary analysis will include assessment of baseline comparability between the two treatment groups. If needed, additional models will be developed to adjust for inequalities not adequately controlled by the randomization process. Results will be reported as the hazard ratio comparing the 2 groups. Survival analyses will also be controlled for unequal follow up periods between subjects. As such, the number of subjects available at annual time points will be reported, along with the Kaplan-Meier probability and associated 95% confidence intervals. It is assumed that subjects censored early will have the same probability of disease at each time point as those with longer follow up. To examine this assumption, relevant baseline characteristics will be compared between subjects enrolled in the first half of the study with those enrolled later. If the 2 cohorts are similar, we can expect that the survival probabilities are valid even with difference in follow up. Disease free survival will also be examined between the two cohorts.

Additional analysis will be presented separately for adjudicated CMV disease and investigator-determined CMV disease. For this analysis the entry point will be date of transplant and the endpoint will be the date of onset of CMV disease as determined by the endpoint committee and a similar comparison in which the end point is the onset of CMV disease as determined by the investigator. The study groups will be again be compared using the non-

stratified log rank test, as well as the stratified log rank test for each stratum separately (receipt of induction antilymphocyte antibodies and renal dialysis).

12.7.1.2 Composite disease free survival

A Kaplan-Meier survival probability will be calculated for each regimen. The starting point will be the day of transplant; the end point will be the date of onset of CMV disease or date of death. Subjects will be censored at date of last follow up if lost to follow up, withdrawal or at end of study. The equality of the two survivor functions will be compared using a rank sum test for both the nonstratified grouping and the stratified by receipt of antilymphocyte induction therapy and renal dialysis.

12.7.1.3 CMV resistance

For CMV resistance testing performed in subjects with CMV disease, the incidence of resistance as assessed by proportion of subjects with UL97 and UL54 mutations will be compared between the two study arms. The resistance will be categorized as present or absent and compared between the 2 groups using a Fisher exact test. In pre-emptive therapy subjects showing increase or no decline in CMV PCR quantitation following receipt of valganciclovir but no evidence of CMV disease, the incidence of resistance (UL97 and UL54 mutations) will be categorized.

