7.6.5 CMV resistance testing

Study day 1 – 12 month

(This one time study visit may occur at any time point throughout the 12 month duration of the study)

For those subjects who demonstrate no reduction in viral load after three weeks of ganciclovir/valganciclovir employed for CMV viremia in the preemptive therapy group or for the treatment of CMV disease in subjects in either study group, assessment of genotypic resistance for UL97 and UL54 mutations may be undertaken. This blood sample will be obtained at the transplant center if hospitalized. If discharged, blood may be collected during routine follow-up clinic appointments, at outpatient laboratories, skilled nursing facilities, or rehabilitation facilities. Resistance testing will be completed at the University of Washington virology laboratory. All materials, shipping supplies, and instructions will be provided to the remote location. Please see laboratory manual for all process and storage directions.

7.7 Non-laboratory Procedures and Clinical Assessments Schedule (see also Schedule of Procedures appendix A)

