8.2.4 Special Assays or Procedures

8.2.4.1 CMV resistance to ganciclovir

(as needed during study day 1-365)

For those subjects who demonstrate no reduction in viral load after three weeks of ganciclovir/valganciclovir employed for CMV viremia in subjects in the preemptive therapy group or for the treatment of CMV disease in subjects in either study group, assessment of genotypic resistance for UL97 and UL54 mutations may be undertaken. Testing may also be undertaken within the 3 weeks at the request of the site investigators after discussion with the study PIs if the viral load fails to decline or if there is lack of response to the treatment of CMV disease. Please see section 7.5.5 for sample collection for resistance assays. Testing will be performed at the Central Virology lab (U. of Washington Virology Lab). Testing for UL97 and UL54 mutations conferring resistance to ganciclovir will be performed in a step-wise manner. If genotypic resistance to UL97 is not found, then no further testing will be undertaken. If UL97 mutation conferring resistance is found then reflexive UL 54 genotyping will be performed. Results of genotypic testing will be reported back to the investigators, approximately within one month of assessment. The decision to treat resistant CMV, the choice of anti-CMV agent for treatment, the duration of therapy and subject follow up will be in accordance with standard practice at the site

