12.8 Interim and Final Analysis

12.8.1 Interim analysis

There will be a single planned interim analysis for the primary endpoint of CMV disease. This analysis will be done after 1/3 of the subjects or 60 subjects have been enrolled and followed for 1 year. Additional endpoint analysis would introduce a multiple comparison bias with a resultant "alpha penalty". Each test done at $\alpha=.05$ means that roughly 5% will generate a type 1 error [rejecting the null hypothesis when in fact it is true]. Repeated testing of interim data can therefore inflate false positive error. To account for this loss of alpha, the sample size would need to be up-adjusted making the study infeasible. For the planned interim analysis, we will use alpha preservation estimation for repeated assessments [Method of

Haybittle-Peto] so that the trial will be terminated only if there is a statistically significant difference in the incidence of CMV disease at the 0.001 level. A statistically significant difference in the incidence of CMV disease at this level [.001] would be detectable after the enrollment of 60 subjects with 1 year follow up, if the difference in the incidence of CMV diseases between the two groups is greater than 50%.

12.8.2 Interim analysis showing futility:

It is possible that the interim analysis could suggest the likelihood of futility i.e. the trial may result in equivalence or non-inferiority. However, there will be no stopping rule for futility. Even if the interim analysis shows that the two groups are equivalent in efficacy with regards to CMV disease rate, there are additional benefits of continuing the trial for example, cost effectiveness of the two approaches which has societal benefits and wider implications. Additionally, differences in immunologic parameters, opportunistic infections, survival, graft loss, and drug resistance have profound relevance for advancing the field. The study will therefore continue so that these additional assessments can be systematically conducted.

12.8.3 Final analysis:

This will be completed when all subjects who have not previously discontinued have completed the one year follow up study visit. Primary, secondary and selected exploratory analyses (outlined in section 12.7) will be performed after one year follow up with supplementary analyses of exploratory endpoints (outlined in section 12.7) performed at study closure (and no longer than 7 years after first enrollment).

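### The arm comparison of ganciclovir resistance (12.7.1.3, exploratory) is made only among tested subjects with CMV disease, so it does not estimate the incidence of resistance by strategy

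*Combined protocol and SAP*

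**What the plan says.** - **Comparison (12.7.1.3).** The section begins "For CMV resistance testing performed in subjects with CMV disease, the incidence of resistance as assessed by proportion of subjects" with UL97 and UL54 mutations. Resistance is scored present or absent and "compared between the 2 groups using a Fisher exact test".
- **Viremia without disease (12.7.1.3).** A separate sentence covers preemptive subjects "showing increase or no decline in CMV PCR quantitation following receipt of valganciclovir but no evidence of CMV disease". For them, "the incidence of resistance (UL97 and UL54 mutations) will be categorized". It gives no denominator, no pooling with disease cases and no per-arm total.
- **Who is tested (7.6.5, 8.2.4.1).** There are two triggers: viremia not responding to treatment in the preemptive arm, and treated CMV disease not responding in either arm. Testing is optional: "assessment of genotypic resistance for UL97 and UL54 mutations may be undertaken". Footnote 8 of Appendix A can be read as allowing it in any disease case.
- **Surveillance (7.5.3.2, 8.2.3).** Scheduled CMV PCR is done in the preemptive arm only.
- **Step-wise genotyping (8.2.4.1).** "If genotypic resistance to UL97 is not found, then no further testing will be undertaken".
- **Planned rates (12.1).** CMV disease is assumed in 20% of the prophylaxis arm and 5% of the preemptive arm, with 80 per arm.
- **Status.** Resistance is not listed in 3.2.3. It appears only under the exploratory analyses in 12.7. Section 12.8.2 nevertheless includes it in a list of differences worth continuing for: "survival, graft loss, and drug resistance have profound relevance for advancing the field".

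**The concern.** The section calls the quantity an incidence and compares it between arms, but its denominator is formed after randomization by the primary outcome. The two strategies are expected to produce very different numbers of disease cases, so the groups compared are no longer the randomized groups. Section 2.2 describes a strategy trial. The matching question is how often resistance is found per subject assigned to each strategy, and no resistance analysis uses all randomized subjects.

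Resistant viremia found in a preemptive subject before disease cannot change the test, however often it occurs. A reader who takes the Fisher result as the resistance cost of each strategy would be reading a different quantity.

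**Working it through.** **1. The plan's own figures.** Expected cases at 80 per arm are 80 × 0.20 = 16 and 80 × 0.05 = 4. The total of 20 matches the events in the 12.1 table. Exact power of the two-sided Fisher test for 20% versus 5% at 80 per arm is 79.3%, in line with the stated 80%. At the minimum enrollment of 176 (88 per arm), cases are 88 × 0.20 = 17.6 and 88 × 0.05 = 4.4, about 18 and 4. These are upper limits on the Fisher denominators at the planned rates, because testing is optional and is triggered mainly by non-response.

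**2. What is estimated.** Let d be the probability of disease and r the probability of resistance given disease, in one arm. With every case tested, the planned comparison concerns r. Resistant disease per randomized subject is d × r. The documents give no resistance rate, so the values below are assumptions.

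| Assumption | Planned comparison (prophylaxis vs preemptive) | Per randomized subject |
|---|---|---|
| r = 10% in both arms | 10% vs 10% | 0.20 × 0.10 = 2.0% vs 0.05 × 0.10 = 0.5% |
| d × r = 2% in both arms | 0.02/0.20 = 10% vs 0.02/0.05 = 40% | 2% vs 2% |

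The factor separating the two scales is the ratio of disease rates, 0.20/0.05 = 4. It does not depend on the assumed resistance level. Across the rate pairs in the 12.1 table it runs from 20/7.0 = 2.9 to 4.

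**3. Resistance without disease.** Take 88 per arm and assume 2 resistant prophylaxis disease cases and no resistant preemptive disease cases. The planned comparison is 2/18 (11.1%) versus 0/4, p = 1.00. It stays there whether 0, 3, 6 or 8 viremic preemptive subjects without disease are resistant. Detected resistance per randomized preemptive subject moves over the same range from 0/88 to 3/88 (3.4%), 6/88 (6.8%) and 8/88 (9.1%), against 2/88 (2.3%) in prophylaxis.

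**4. Information in the planned test.** With 16 and 4 cases, all tested, and 0/4 resistant in the preemptive arm, p ≤ 0.05 needs at least 11/16 resistant in prophylaxis (10/16 gives p = 0.087). Exact power is about 12% for 10% versus 30% resistant among cases, and about 33% for 10% versus 50%.

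**5. The marker.** Section 12.7.1.3 counts UL97 and UL54 mutations without saying whether either or both define resistance as present. Under 8.2.4.1 a sample with no UL97 resistance is not sequenced for UL54. UL97 status is therefore known for every tested sample, and UL54 status only where UL97 resistance was found.

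**The case against.** The strongest defense is that CMV disease is the one testing indication the arms share. Viremia-triggered testing and surveillance PCR exist only in the preemptive arm, so viremic subjects without disease have no counterpart under prophylaxis. Keeping them out of an inferential comparison is sound. This stands, and it limits the remedy. A reader might infer that the answer is an intention-to-treat test of any detected resistance. The documents do not support that. Such a test would count two indications in one arm and one in the other, and resistant viremia without disease under prophylaxis could go undetected and score as zero.

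A reader might also infer that the plan ignores resistance in viremic preemptive subjects. It does not: it categorizes it, outside the comparison. Nor does continuing the trial turn on this test. Section 12.8.2 has no futility rule, leads with cost effectiveness, and names resistance as one item in a longer list.

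Finally, resistant disease per randomized subject partly repeats the primary result, because it is the product d × r. That is true, and it is the reason to keep the proportion among tested cases as a descriptive companion. None of this makes that proportion an incidence by strategy.

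**Conclusion.** The concern holds as a matter of denominator and label. The planned comparison estimates resistance given disease and testing. At the planned rates it rests on at most about 16 versus 4 cases, and it differs from the per-randomized comparison by a factor of up to four. The factor rests on the 12.1 disease rates and on testing of all cases; optional testing makes the compared set smaller and less well defined.

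Two stronger readings go too far. One is that the planned test would point the wrong way. It can be made to: with 2 and 1 resistant cases it reads 2/16 (12.5%) versus 1/4 (25%), against 2/80 (2.5%) versus 1/80 (1.25%) per randomized subject. But the counts are invented and the p-values are 0.51 and 1.00, so this shows what is possible, not what is expected. The other is that UL54-only mutations will be recorded as absent. Section 12.7.1.3 does not say how an unsequenced UL54 is coded, and the documents do not say how often it would matter. What stands is that the label does not match what is sequenced.

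The analysis is exploratory and outside the 3.2.3 list. The change is worth making because it is cheap; no primary or secondary result depends on it.

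**What to change.** In 12.7.1.3:

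- **Comparison.** Compare CMV disease with detected resistance, to 12 months, per randomized subject (ITT), using an exact test and a confidence interval for the difference.
- **Descriptive per-arm count.** Report all detected resistance, with or without disease, per randomized subject by arm. Tabulate numbers eligible, tested and resistant by arm and indication. State that prophylaxis subjects have no viremia surveillance or viremia-triggered testing and that testing is optional.
- **Conditional proportion.** Keep the proportion resistant among tested disease cases as descriptive.
- **Marker.** Define present as UL97 resistance, and report UL54 only among UL97-positive samples.

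The cost is SAP wording and one table, with no new samples or assays. The downside is that untested subjects count as without detected resistance and events will be few, so the result carries descriptive weight.
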